The IAC will also provide a further layer of overall supervision for the study and ensure that it is being conducted in accordance with the protocol, the principles of Good Clinical Practice and other relevant regulations. The IAC will meet face-to-face or via teleconferencing at the start of the project and every twelve months thereafter.

The specific tasks of the IAC include:

- To agree the study protocol and any protocol amendments.
- To resolve problems brought to it by the WOLVERINE study management group.
- To provide advice to the investigators on all aspects of the study.

ETHICS & CONSENT

Patients will not undergo any additional investigations for the purposes of this study. Clinical follow-up will be limited to review of health records up to a maximum of 30 days postoperatively.

Additional patient contact (telephone, in-person, by email or by application) will take place between 30 days postoperatively and one year postoperatively to collect patient data.

The cohort study will be conducted and reported according to STROBE (Strengthening the Reporting of Observations studies in Epidemiology) guidelines.

DATA MANAGEMENT

Principal investigators at each participating site are responsible for obtaining necessary local approvals. Data will be collected in two phases. During the index admission, pre-operative and intra-operative data will be collected. Local Principal Investigators will establish pathways in their hospitals to ensure robust data collection; for example, pre-operative data could be collected in the morning prior to surgery, with intra-operative data fields completed in theatre immediately following completion of the procedure. Alternatively, all index data including patient registration could be collected in theatre, or in the post-operative ward.

Collection of post-discharge follow-up data

Patients who are discharged from hospital early may be more likely to develop a surgical site infection out of hospital and often fail to be noted or registered. A review of the participating patients' clinic visit notes and letters will therefore be mandatory for all participating hospitals. All

patients will be followed-up to a maximum of 30-days postoperatively (with Day 0 being the day of surgery) by a review of their inpatient health records, routine clinic visit notes/letters, and reports for postoperative radiological investigations arranged as part of normal patient care. The study is designed efficiently so that existing patient follow-up pathways and health records can be used, with only data that is routinely collected as part of normal clinical care being captured.

Patient reported outcomes.

After completing informed consent, the patient will be sent a link by email, mobile phone or text to report outcomes in REDCAP. Consent for the cohort study can be obtained either before or after surgery, unless local ethics guidance stipulates otherwise.

DATA HANDLING AND RECORD KEEPING

Source Data

Source data within the study will be kept as part of the participants' medical notes generated and maintained at site. As all clinical data collected and analysed within the study are routinely gathered in clinical practice, source data will be within the medical notes.

The patient-completed questionnaires form source data. As these are completed online via the WOLVERINE REDCap database, this data will form part of the source data.

Data Management

Information will be collected at the following times:

- At baseline (surgeon level)
- At 30 days after the operation (surgeon level)
- At 30 days after the operation (patient level)
- At 60 days after the operation (patient level)
- At 90 days after the operation (patient level)
- At 6 months after the operation (patient level)
- At one year after the operation (patient level)

Data will be entered directly onto the secure electronic REDCap database by members of the research team and by participants.

Site study collaborators will be provided with a paper copy of the eCRF to facilitate data collection. If this is used, they should then transfer data from the paper CRF into the online database (https://www.bistc.redcap.bham.ac.uk). Data management staff will check all incoming data CRFs for completeness, data consistency and compliance with the protocol. If discrepancies or missing data are identified, the data management staff will raise queries with the research team at the participating hospital via the study database.

Data Security and Data Protection

The security of the Study Database System is governed by the policies of the University of Birmingham. The study database will be hosted on the REDCap system managed and maintained by BiCOPS..

Data management and data security within BiCOPS will abide by the requirements of the General Data Protection Regulations (GDPR) and any subsequent amendments. The study will be conducted at collaborating sites in accordance with the country-specific data protection requirements.

Access to data will be restricted by usernames and passwords, at participating sites. Each participant will be allocated a unique study number at entry. All communication will use this as the identifier. All data will be analysed and reported in summary format. No individual will be identifiable.

Archiving

It is the responsibility of the PI to ensure all essential study documentation and source documents (e.g. Investigator Site Files, participants' hospital notes, copies of CRFs) at their site are securely retained for the contractual period. Archiving will be authorised by BiCOPS on behalf of UoB following submission of the end of study report. No documents should be destroyed without prior approval from the BiCOPS director.

The electronic TMF will be stored at BiCOPS for at least 3 years after the end of study. Long-term offsite data archiving facilities will be considered for storage after this time, data will be stored securely and confidentially for 10 years in accordance with the UoB Code of Practice for Research.

QUALITY CONTROL AND QUALITY ASSURANCE

Site set-up and site initiation

Once a site has local approvals in place and is nearly ready to open for recruitment, the final step will be to undertake a brief remote site initiation visit (SIV) via teleconference or videoconference. These SIVs will be run by central WOLVERINE study team members and may be conducted enbloc with other sites at a similar stage of readiness to enhance efficiency. The SIV will cover details of local recruitment pathways, consent processes, data flow, and overall study conduct.

Investigator agreement form

Prior to opening, all participating local Principal Investigators will sign an Investigator's Agreement with the University of Birmingham to document acceptance of the responsibilities of the PI at the site.

Monitoring

Monitoring will be via data validation and range checks built into the REDCap database used to collect and manage the data; statistical monitoring techniques will be used to compare data from different sites to identify sites that may warrant further investigation, site monitoring and/or support and training. Review by the study oversight committees will also include the review of completion of primary and secondary outcomes.

Study staff from UoB will be in regular contact with the site research teams to check on progress and address any queries that they may have.

The Data Management Committee will check submitted CRFs from the participating hospitals for compliance with the protocol, data consistency and missing data. They will send participating hospitals data queries for missing data or clarification of inconsistencies or discrepancies.

END OF STUDY DEFINITION

Study participants will be followed-up by patient-completed questionnaires until 12-months post-surgery. Clinician-reported outcomes will be collected up to 30 days post-operatively. The end of study will be when the last enrolled participant completes their 12-month questionnaires, all database queries have been resolved and the database has been locked and analyses completed. The WOLVERINE Study Office will notify the REC and Sponsor within 90 days of the end of study. The WOLVERINE Study Office will provide the REC and Sponsor with a summary report of the study.

CONFIDENTIALITY AND DATA PROTECTION

At study entry, study participants will be asked for consent for the UoB to collect/hold their email address and mobile phone number. These identifiable details will be used by the central coordinating centre to contact participants to remind them to complete follow-up questionnaires and to obtain corresponding clinical data from the participant's treating centre.

Email addresses and mobile phone numbers will be deleted upon completion of the final study analysis. All data collected about participants will be identified using only the unique WOLVERINE study REDCap ID code.

Any correspondence between the WOLVERINE study office and hospital sites will use the anonymous ID code only.

Wolverine Protocol IRAS: 334321

The linkage between the study ID code and participants will be maintained in strict confidence at participating sites. This data will not be submitted to the WOLVERINE study office and will not be sent outside of the participating site.

Confidentiality of all participant's data will be maintained and there will be no disclosure of information by which participants may be identified to any third party other than those directly involved in the treatment of the participant.

Finance

WOLVERINE is an investigator-initiated and investigator-led study. The study has been funded by the ESCP through an unrestricted educational grant received from Ethicon.

INSURANCE AND INDEMNITY

The University of Birmingham has in place Clinical Trials indemnity coverage for UK sites for this study which provides cover to the University for harm which comes about through the University's, or its staff's, negligence in relation to the design or management of the study. For non-UK sites the University of Birmingham has in place a worldwide public liability policy.

The risk of the trial is no greater than the risk of the standard clinical care. Responsibility for the participants at sites remains with the organisation responsible for the clinical site and it is therefore indemnified through their normal arrangements.

PUBLICATION POLICY

The output from this research will be published under a single corporate authorship group: "European Society of Coloproctology (ESCP) collaborating group", manuscripts and authorships will be separated for those who contributed to the audit study and those who contributed to both the audit AND the cohort study. The following roles will be recognised within the collaborating authorship list: Study Protocol Writing group, Study Management Group, Data Management Committee, Statistical analysis, ESCP Cohort Studies and Audits Committee, ESCP Research Committee, study coordinators, Principal Investigators, co-Principal Investigators, Collaborators.

Specifically each participating hospital may include up to five collaborators for publication(s) regarding the audit study, and up to five (different or identical) collaborators for the (long term follow-up) of the cohort study on the condition that data for at least 10 consecutive patients is entered with at least 95% data completeness: the Principal Investigator; the surgical associate co-Principal Investigator; and three further collaborators supporting study delivery and data collection. An increase in the number of collaborators at a participating hospital is theoretically

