Abdominal wound dehiscence (also referred to as 'evisceration' or 'fascial dehiscence'). Defined as an unintended acute wound failure at the level of the fascia and a postoperative complication after primary closure of a laparotomy incision.

Degree of contamination during surgery

Clean: an incision in which no inflammation is encountered in a surgical procedure, without a break in sterile technique, and during which the respiratory, alimentary and genitourinary tracts are not entered

Clean-contaminated: an incision through which the respiratory, alimentary or genitourinary tract is entered under controlled conditions but with no contamination encountered

Contaminated: an incision undertaken during an operation in which there is a major

break in sterile technique or gross spillage from the gastrointestinal tract, or an incision in which acute, non-purulent inflammation is encountered. Open traumatic wounds that are more than 12 to 24 hours old also fall into this category

Dirty: An incision undertaken during an operation in which the viscera are perforated or when acute inflammation with pus is encountered during the operation (for example, emergency surgery for faecal peritonitis), and for traumatic wounds where treatment is delayed, and there is faecal contamination or devitalised tissue present.

Early abdominal wound failure. Defined as surgical site infection, surgical site occurrence or abdominal wound dehiscence diagnosed within 30 days postoperatively.

Incisional hernia. Defined by the European Hernia Society as "any abdominal wall gap with or without a bulge in the area of a postoperative scar perceptible or palpable by clinical examination or imaging".

Late abdominal wound failure. Defined as surgical site infection in presence of foreign body material or incisional hernia at one year postoperatively.

SSI: Surgical Site Infection. Defined by the CDC (Centers for Disease Control and Prevention) as infections related to a surgical procedure that occur near the surgical site within 30 days following surgery (or up to 1 year following surgery where synthetic implants are involved).

SSO: Surgical Site Occurrence. Defined as: wound cellulitis, non-healing incisional wound, skin or soft tissue ischemia, skin or soft tissue necrosis, serous wound drainage, stitch abscess, seroma, hematoma, infected or exposed mesh, surgical site infection, abdominal wound dehiscence.

INTRODUCTION

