Several large prospective studies have reported on varying closure techniques and their impact on incisional hernia rates. The 2015 STITCH trial, compared small and large suture bites in abdominal wound closure (19). The authors observed that those with small bites had a lower risk of incisional hernia at one year follow-up. Alternatively, the PRIMA trial compared primary abdominal fascial closure to standard closure plus prophylactic mesh (onlay or sublay). These studies demonstrated that prophylactic onlay mesh significantly reduced incidence of incisional hernias (20). These studies have had several critiques and caused substantial debate in surgical communities across the world. Additionally, the studies to date have considerable heterogeneity and limited QoL outcome data. The Match review, a meta-analysis and systematic review aimed to evaluate fascial closure materials and techniques for emergency and elective laparotomies was published in 2015 (21). Although the authors found significant heterogeneity between included studies, small bites and stitches that absorb slowly seemed to have advantages in incisional hernia prevention. The most recent guidelines of the European Hernia Society (EHS) reflect these findings, as the current recommendation of the society is to close the fascia with a continuous, small bite, slowly absorbable suture. Most of the recommendations in these guidelines, however, rely on low to moderate quality evidence (22).

The aim of this current study is to provide global real-world data on patients, disease and operation-related factors and outcomes, which will also serve as benchmark data to set up a future interventional study on abdominal wound closure and SSI prevention.

STUDY RATIONALE

Need for research

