The parallel prospective audit study will result in the generation of a large, international dataset of real-world data on wound closure and SSI prevention practices for patients undergoing abdominal surgery, and enable the first description of the global variability in practice.

This dataset will be used to explore how differences in patients, treatment practices and preventative measures may be associated with different clinical and patient-reported outcomes. The datasets will be analysed separately. They cannot fully control for selection bias and interaction effects; as such, they create hypothesis-generating information rather than true evidence of effect. The data collected as part of this study will be used to inform the design of a future interventional study on abdominal wound closure and SSI incidence in the elective and expedited/emergency general and colorectal surgery patient populations.

AIMS & OBJECTIVES

Main research question:

1. What is the relationship between differing wound closure materials and techniques, with the occurrence of early and late abdominal wound failure?

Abdominal wound failure includes surgical site infections according to Center for Disease Control classification, surgical site occurrences (which will be described excluding SSI,

Wolverine Protocol IRAS: 334321 version 1.0 dated 30 January 2024

abdominal wound dehiscence), abdominal wound dehiscence with or without evisceration, and incisional hernia formation. (24) Abdominal wound dehiscence (also referred to as 'evisceration' or 'fascial dehiscence') is an unintended acute wound failure at the level of the fascia and is a postoperative complication after primary closure of a laparotomy incision. (25) Incisional hernia is an example of late abdominal wound failure, occurring up to 65% in high-risk groups and up to at least 10 years after surgery (*long term follow-up of the PRIMA trial, accepted for publication in the Lancet.* (26) It was defined by the European Hernia Society as "any abdominal wall gap with or without a bulge in the area of a postoperative scar perceptible or palpable by clinical examination or imaging". (27, 28)

Further research questions:

- 1. What is the relation between early abdominal wound failure and late abdominal wound failure?
- 2. What is the impact of late abdominal wound failure, including incisional hernia, on the patient's quality of life?
- 3. What are the rates of early and late abdominal wound failure?

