- 4. What are the effects of SSI prevention measures on the incidence of early and late abdominal wound failure?
- 5. What is the impact of a minimally invasive technique vs. open technique on the incidence of early and late abdominal wound failure?
- 6. What is the impact of early and late abdominal wound failure on the patient?
- 7. What is the impact of early and late abdominal wound failure on the duration of postoperative stay and the number of outpatient visits and unscheduled hospital visits?
- 8. What are the early and late abdominal wound failure associated costs (eg, hospital/ICU stay, unscheduled hospital visits and patient reported expenses)?
- 9. Which risk scores will have the highest predictive value for our primary outcomes within this cohort?

Summary of the cohort study key objectives

Short term:

Assessing the different practices of wound closure and surgical site prevention globally

Assessing the effect of wound closure and surgical site infection prevention practices on the incidence of abdominal wound failure at 30 days.

Longer-term:

Early phase: 30 days to 90 days
Assessing the different practices of abdominal wound closure and surgical site prevention globally and their effect on wound healing, SSI, patient recovery and return to normal function.

Later phase: 90 days to 1 year
The incidence of abdominal wound failure, including the development of incisional hernia.

Overall:

Exploring the relationship between early adverse wound outcomes and longer-term patient-reported incisional hernia occurrence.

Comparison of quality of life for patients with and without wound healing issues and/or incisional hernia.

Key outcome measures

Short term:

Methods of Wound Closure:

- Types and techniques of fascial, subcutaneous and skin closure
- Incidence and types of mesh use
- Use of SSI Prevention measures
- Incidence of abdominal wound failure at 30 days
- Length of postoperative stay
- Reoperations within 30 days
- 30-day mortality
- SSI diagnosis or management requiring ICU admission
- Unplanned readmissions within 30 days
- Need for interventional radiology procedures within 30 days
- Abdominal wound dehiscence within 30 days

Long-term:

Patient-reported outcomes and quality of life from 30 days to 1 year post-operation

At all time points:

- EQ5D-5L
- SF-12

Early phase [wound healing / SSI / return to normal function]: 30 days to 90 days

- Bluebelle wound healing questionnaire at 30 days

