The patient will be provided with a unique patient identification number by the person discussing the study with them (this is taken from the site-specific WOLVERINE REDCap LINK SHEET provided by the study office). This unique identifier will be recorded on the WOLVERINE PIS. Eligible patients will also be provided with a generic QR code. This QR code and unique identifier will be used by the potential participants to access the REDCap-WOLVERINE system and the consent form.

The potential participant will then be asked to access the online system at a time convenient to them, i.e. they do not need to access the system whilst in hospital. Upon access of the online REDCap system, they will be asked for consent for follow-up.

This unique REDCap ID will be the only identifier used to identify the patient in any correspondence between the coordinating centre and the participating site.

*Participating sites may download the consent form as a PDF if required for the WOLVERINE Site File.

STUDY FOLLOW-UP

Follow-Up Time points

After the baseline visit, there are no further study-specific visits. All study-specific follow-up is conducted via remote reporting.

There are 5 follow-up time points: 30-, 60- AND 90-days post-surgery; 6 months and one year post-surgery.

Short-term follow-up: 30-days post-surgery

- Clinician reported:
 - o Conducted without the need for patient attendance.
 - No specific follow-up visit is mandated for participants.
 - The 30-day post-surgical outcomes form is undertaken by the clinical team, with routinely collected information from patient notes or electronic records, or other routinely collected data sources.
- Patient reported
 - Data is collected remotely from the participant via the WOLVERINE online REDCap system
 - Bluebelle wound healing questionnaire, EQ-5D5L, SF-12, the Patient reported Wound Recovery PROM QoL and the ESCP Incisional Hernia PROM.

Longer-term follow-up

At the 60-days, 90-days, 6-month and 1 year post-operative timepoints, data is collected remotely from the patient only. The following questionnaires will be requested:

- The EQ-5D5L and the SF-12 at each of the 4 timepoints.
- Bluebell wound healing questionnaire at 30 days.
- Patient reported Wound Recovery PROM at 60 days and 90 days.
- ESCP incisional hernia PROM at 3-, 6- and 12-months.
- HerQles questionnaire at 1 year

^{**}There is no clinical team involvement beyond 30-days post-surgery.

COHORT STUDY SCHEDULE OF EVENTS

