		WOLVERINE COHORT STUDY								
		Study entry	Baseline data	After Surgery	30-day follow- up	30-day PROM	60-day PROM ER DATA	90-day PROM	6-month PROM	1-year PROM
Oliveinian	Patient information		√			PROM NO FURTH	CTION AI	JOIT		
Clinician reported audit	Surgery information			>	1	NO COLLE	DAYS			
- all patients	Short-term Complications / reinterventions				✓					
Patient reported cohort	Informed consent	√								
study – only patients	Wound healing questionnaire (Bluebelle)					√				
who provide consent, recorded	Patient reported Wound Recovery PROM					1	√ if wound unhealed	√ if wound unhealed		
via online PROMS system	ESCP incisional hernia PROM							√	1	√
N.B -	HerQles questionnaire									√
IN ADDITIO N to the clinician-reported patient-level audit data	EQ-5D-5L					√	✓	√	√	√
	SF-12					√	√	√	√	√

PROMS targets for:

- 30 days -> 90 days
 - o SSI, wound healing, return to normal function, patient satisfaction
- 90 days -> one year

 wound integrity, reintervention or readmission, incisional hernia, patient satisfaction

PATIENT WITHDRAWAL

Patients are free to withdraw from the study at any point and will be made aware from the beginning of their involvement in the study that they can withdraw at any time. Participants are given details on how to withdraw from the study in the Patient Information Sheet Before the start of each follow up questionnaire patients will be asked if they are happy to continue participating in the study.

Reasons for Withdrawal

Patients are free to withdraw from participation in the study at any time upon request.

An investigator may terminate a study subject's participation in the study if:

- Any medical condition, event or situation occurs such that continued participation in the study would not be in the best interest of the subject.
- The subject meets an exclusion criterion

Other reasons for withdrawal:

Inability to contact the patient

Handling of Subject Withdrawals

If a patient withdraws from the study, then their record on REDCap will be closed and no further data will be collected. All data collected until that timepoint will be retained and these patients will be included in baseline analyses and reports.

SAFETY CONSIDERATIONS

There are no anticipated safety considerations relating to the WOLVERINE study. There is no risk of harm to either patients or investigators.

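### Late wound failure is defined by examination, imaging and CDC criteria, but after day 30 only patient questionnaires are collected, and no listed questionnaire covers infection after day 90

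*Protocol*

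**What the plan says.** **Definitions.** The protocol's list of definitions takes incisional hernia from the European Hernia Society (EHS): "any abdominal wall gap with or without a bulge in the area of a postoperative scar perceptible or palpable by clinical examination or imaging". The entry for late abdominal wound failure reads: "Defined as surgical site infection in presence of foreign body material or incisional hernia at one year postoperatively". Surgical site infection (SSI) follows CDC criteria, with the window extended "up to 1 year following surgery where synthetic implants are involved". The Aims & objectives section repeats the EHS definition under the main research question and adds: "Abdominal wound failure includes surgical site infections according to Center for Disease Control classification".

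**Use.** The main research question relates closure materials and techniques to early and late failure, and further question 3 asks for the rates of both. The later-phase objective asks for the incidence of wound failure, hernia included, from 90 days to one year.

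**Data after day 30.** Study follow-up states: "There is no clinical team involvement beyond 30-days post-surgery". Ethics & consent limits record review to 30 days and excludes study-specific investigations. The End of study definition stops clinician-reported outcomes at 30 days. In the schedule of events, the hernia questionnaire is given at 90 days, 6 months and one year, and HerQles at one year. Bluebelle is given at 30 days only. The Wound Recovery questionnaire is given at 30 days and repeated at 60 and 90 days if the wound is unhealed. The listed questionnaire targets from 90 days to one year are "wound integrity, reintervention or readmission, incisional hernia, patient satisfaction".

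**Acknowledgement.** One overall objective refers to "longer-term patient-reported incisional hernia occurrence". The protocol summary places one-year hernia among the patient-reported outcomes, and Key outcome measures names the hernia questionnaire as a late-phase measure.

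**The concern.** The two components of late failure have different problems. Hernia is measured by something other than its definition: a patient's answer stands in for an examination or a scan. The definition also counts gaps without a bulge, which a patient may not notice. Infection with foreign material is part of the outcome for a full year, yet nothing listed asks about it in the last nine months.

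A statistical analysis plan cannot repair either problem, because it cannot supply data that were not gathered. Late failure appears in the main question and in further questions 1 to 8, as outcome or as exposure. If results are reported under the stated definition, the rate and every association will be read as clinically ascertained hernia and CDC infection when they are not.

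**Working it through.** **1. Definition against data source**

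| Component | Definition requires | Collected, day 31 to 90 | Collected, day 90 to one year |
|---|---|---|---|
| Incisional hernia | Finding on examination or imaging | Hernia questionnaire at 90 days | Hernia questionnaire at 6 and 12 months; HerQles at 12 months |
| SSI with foreign material | CDC criteria, up to one year | SSI is a stated target; Wound Recovery questionnaire at 60 and 90 days if unhealed | SSI not among the targets; no wound questionnaire listed |

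No cell in the last two columns contains an examination, a scan or a record review. Ethics & consent and the analysis plan do mention telephone or in-person contact after day 30. That sits awkwardly with the remote-only follow-up section, but it concerns contact to collect patient data and specifies no examination.

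**2. Timing.** The glossary fixes late failure at one year. The later-phase objective asks for incidence over 90 days to one year. Take a patient who reports a hernia at 6 months and has it repaired before month 12. Under incidence over the period, the patient counts. Under status at one year, the patient may not. The protocol does not say which applies.

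**3. Size of the hernia problem (illustration).** There is no figure in the plan to reproduce: the 1,000 patients are a recruitment projection, and no hernia rate is assumed. The protocol gives no sensitivity (Se) or specificity (Sp) for the hernia questionnaire, so the values below are assumptions. The assumed true risks are 10% and 15%, a risk ratio of 1.50, with the same error in both groups.

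Apparent rate = p × Se + (1 − p) × (1 − Sp).

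| Se / Sp | True 10% appears as | True 15% appears as | Apparent risk ratio |
|---|---|---|---|
| 0.60 / 0.98 | 0.060 + 0.018 = 7.8% | 0.090 + 0.017 = 10.7% | 1.37 |
| 0.60 / 0.95 | 0.060 + 0.045 = 10.5% | 0.090 + 0.0425 = 13.25% | 1.26 |
| 0.90 / 0.95 | 0.090 + 0.045 = 13.5% | 0.135 + 0.0425 = 17.75% | 1.31 |
| 0.80 / 0.90 | 0.080 + 0.090 = 17.0% | 0.120 + 0.085 = 20.5% | 1.21 |
| 0.70 / 0.85 | 0.070 + 0.135 = 20.5% | 0.105 + 0.1275 = 23.25% | 1.13 |

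For comparison, the half-width of a 95% interval around 10%, if all 1,000 patients answered and clustering by hospital is ignored, is 1.96 × √(0.10 × 0.90 / 1000) = 0.0186, or 1.9 points. The error in the rate across the five rows is −2.2, +0.5, +3.5, +7.0 and +10.5 points, so it exceeds sampling error in four of them.

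The shrinkage of the risk ratio comes from imperfect specificity. With Sp = 1 the false-positive term vanishes and the ratio is (0.15 × Se) / (0.10 × Se) = 1.50, unchanged.

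**The case against.** Patient report is disclosed: the summary, the list of outcome measures and one objective all say so, and the glossary merely cites a standard definition. This stands in part. A reader might infer that the protocol hides a substitution, and it does not. What is missing is the link: the definition of late failure, the main question, the rate question and the later-phase objective still rest on the clinical definition.

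Other stronger readings are tempting but not supported:

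- *The rate will be inflated.* The direction is unknown. Low sensitivity with high specificity gives 7.8% for a true 10%, and a definition that includes gaps without a bulge makes under-detection plausible.
- *A hernia repaired before month 12 will be counted as no failure.* That is one reading of the glossary. The incidence wording, the repeated questionnaire, the reintervention target and the mention of person-time and Cox models all point the other way. The conflict is real; its resolution is simply not stated.
- *The biased rate will size the next trial.* The Background says only that the data are those "which will also serve as benchmark data to set up a future interventional study", and the study rationale calls the information hypothesis-generating. No passage says that this hernia rate will set a sample size, so any such calculation would be purely hypothetical.
- *The lack of a misclassification analysis is a defect.* That can be left to the statistical analysis plan, which the protocol promises.

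The questionnaire items are not shown. They may ask about a doctor's diagnosis, a scan or a repair, and the readmission target may pick up some serious infections indirectly. A reported diagnosis is still patient report and misses undiagnosed hernias. A readmission is not an infection under CDC criteria.

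**Conclusion.** The point holds as an internal mismatch that should be corrected. For hernia, the outcome measured is patient-reported while the outcome defined is clinical, and the acknowledgement elsewhere is not carried into the definition or the main questions. For infection, the component appears uncaptured from day 90 to one year by any listed instrument. The counting rule in time is contradictory.

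Remote follow-up is a legitimate design choice; the fault lies in what its result is called. The documents do not fix the size. Over the tabulated assumptions a true 10% appears as 7.8% to 20.5%, and a risk ratio of 1.50 as 1.37 to 1.13, given non-differential error and imperfect specificity. Confidence is high on the mismatch between definition and data source, and does not extend to any particular size or direction of error in the rate.

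**What to change.** - **Hernia.** Define the late outcome as patient-reported incisional hernia by 12 months: positive if reported at any of the 90-day, 6-month or 12-month questionnaires, or if the patient reports a hernia repair. Use this wording in the definitions, the main question, further question 3 and the later-phase objective. Do not report it as hernia meeting the EHS definition.
- **Infection.** Either add a patient-reported wound-infection item at 6 and 12 months, or drop infection from late failure. An added item would not meet CDC criteria either, so it must be labelled patient-reported and not CDC-defined.
- **Timing.** The any-time rule settles the conflict between status at one year and incidence over the period, using questionnaires already scheduled.

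The cost is revised wording and possibly one or two extra REDCap items (infection, and repair if it is not already asked), with no added visits. The downside is a more modest claim: a rate of patient-reported hernia, with late infection either patient-reported or outside the composite.
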